Ten stimuli will be delivered for each ISI and fourteen control MEPs in response to the TS alone will be recorded, for each paradigm, in all participants in a pseudorandomized sequence. The amplitude of the conditioning MEPs will be expressed as a ratio of the mean unconditioned response. The inter trial interval will be set at 5 sec ($\pm 10\%$). All protocols will be performed in a randomized order in all participants. Throughout the experiment, complete muscle relaxation will be monitored by audio-visual feedback where appropriate.

All clinical and, neurophysiological evaluations will be performed at baseline (T0), after 10 tDCS applications i.e. at two weeks (T1), at two months (T2) and at six months (T3).

After the first evaluation (T0), the patients will be divided into two groups randomly. The first group will undergo a tDCS stimulation protocol, while the second group will undergo a placebo (sham) treatment. tDCS will be delivered by a battery-driven

CLINICA NEUROLOGICA - UNIVERSITA' DEGLI STUDI DI BRESCIA
UO Neurologia 2 - AZIENDA SOCIO SANITARIA TERRITORIALE degli SPEDALI CIVILI DI BRESCIA

Direttore: [name]

constant current stimulator (HDCstim, Newronika, Milan, Italy) through a pair of saline-soaked (0.9% NaCl) surface sponge electrodes. The anodes will be placed on the scalp over the motor cortex area and the cathode over the spinal cervical enlargement (over C6) (see Fig. 1B). The electrodes will be secured using elastic gauzes and an electroconductive gel will be applied to electrodes to reduce contact impedance (<5 kΩ for all sessions). During real stimulation a constant current of 2 mA per each anodal electrode (4.0×6.5 cm², current density 0.077 mA/cm²) and 4 mA per cathodal spinal electrode (5.0×7.5 cm², current density 0.107 mA/cm²) will be applied for 20 minutes. For the sham condition, the electrode placement will be the same, but the electric current will be ramped-down 5 seconds after the beginning of the stimulation to make this condition indistinguishable from the experimental stimulation. To detect differences in the perception of the stimulation, patients will be asked whether they thought they were receiving real or sham stimulation at the end of the two-weeks' treatment.

INCLUSION CRITERIA for patients:

- Male or female patients diagnosed with probable ALS, laboratory-supported, or defined according to current clinical criteria (World Federation of Neurology Revised El Escorial criteria - Brooks et al., 2000).

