- Age over 18 years;
- Disease duration ≤ 48 months;
- Score ≥ 2 at the item "swallowing" of the ALS Functional Rating Scale-Revised (ALSFRS-R);
- Score ≥ 1 at the item "walking" of the ALSFRS-R;
- Score ≥ 1 at the item "respiratory insufficiency" of the ALSFRS-R
- Signature of informed consent.

EXCLUSION CRITERIA for patients:

- Motor neuron diseases other than ALS;
- Diagnosis of dementia according to current clinical criteria;
- Severe head trauma in the past;
- Persons carrying static electrical stimulators (e.g. cardiac stimulators, nerve stimulators, auditory implants) that would not work or would be damaged by the magnetic field;
- Persons carrying special metallic foreign bodies (e.g. splinters, some prostheses, screws and nails) that could move if placed inside the magnetic field;
- People with a history of epilepsy or seizures;

CLINICA NEUROLOGICA - UNIVERSITA' DEGLI STUDI DI BRESCIA
UO Neurologia 2 - AZIENDA SOCIO SANITARIA TERRITORIALE degli SPEDALI CIVILI DI BRESCIA

Direttore: [name]

- History of ischemic stroke or hemorrhage;
- Severe comorbidity
- Given that the effects of TMS on the developing fetus are not known, pregnant women will be excluded from the study.

STUDY DESIGN:

This is a non-pharmacological, randomized double-blind controlled clinical trial. This study does not present sub studies. Patients will be randomized into two groups: each group will receive anodal bilateral motor cortex tDCS and cathodal spinal tDCS (real tDCS) or sham stimulation for 5 days/week for 2 weeks, in a 2:1 ratio respectively.

END POINTS:

The long-term effect of tDCS on clinical parameters (ALSFRS-R, ALSAQ-40, CBI, EQ-5D-5L, muscle strength assessed with the MRC scale in different muscle districts), and neurophysiological measures (SICI and ICF).

For efficacy analyses, the primary end point will be the defined as change from baseline in global MRC scores. Secondary end points will be defined as changes from baseline in the ALSFRS-R, ALSAQ-40, EQ-5D-5L, EQ-VAS, CBI and intracortical connectivity (SICI and ICF).

STATISTICAL PLAN:

Parametric analysis (t test) will be used to compare the demographic variables (e.g. age, duration of illness, education) of the various groups at the baseline. A p -value <0.05 will be considered significant.

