In order to estimate the sample size, in order to obtain a significant difference in the primary outcome (Global MRC Score), we performed a "power analysis" based on the effects observed in a small group of patients (pilot study). The "effect size" $f(V)$ was calculated by direct method. Taking into account from previous observations a "partial $\eta^2 = 0.31$, equal to an "effect size" $f(V) = 0.67$ and, considering alpha = 0.05 and the power (1- β) = 0.80, considering a variable as covariate, the sample size expected for two patient groups (real and sham) is 25 total subjects using a repeated-measure ANCOVA study. The proposed sample size of 30 patients should be adequate to achieve the main objective of the study and would allow monitoring for confounding factors or drop-out patients.

Considering the unneglectable number of drop-out patients, that characterize most trials in ALS, we performed intention-to-treat and per-protocol analysis to reduce any bias due to the possible unbalanced drop-out rates between treatment groups. For

patients with missing values, data were assigned using mixed effects models for repeated measures without any ad hoc imputation.

To assess the effect of tDCS treatment on clinical scores over time, we will use a two-way repeated measure ANCOVA with TIME (T0, T1, T2 and T3) as within-subject factors and TREATMENT (sham vs real stimulation) as between-subjects factor, and the baseline values of each score as covariate, to reduce possible effects of baseline impairment on clinical score changes over time.

To assess the effect of tDCS treatment on TMS parameters we will use a two-way mixed ANOVA with TIME (T0, T1, T2 and T3) as within-subject factors and TREATMENT (sham vs real stimulation) as between-subjects factor.

When a significant main effect was reached, *post hoc* tests with Bonferroni correction for multiple comparisons will be conducted to analyze group-differences at respective time points. Mauchly's test will be used to assess for assumption of sphericity, while Greenhouse-Geisser epsilon determination will be used to correct in case of sphericity violation. Spearman's rank-order correlations will be used to assess associations between the improvement in clinical scores and neurophysiological parameters. Statistical analyses will be performed using SPSS version 21 (SPSS, Inc., Chicago, IL, USA).

ETHICAL CONSIDERATIONS (RISK-BENEFIT):

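### SICI and ICF are analysed without the T0 covariate that the clinical scores receive, which costs precision and leaves estimates biased given a chance T0 imbalance

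*Combined protocol and SAP*

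**What the plan says.** - **Endpoint (END POINTS).** SICI and ICF are secondary, and defined as change: "Secondary end points will be defined as changes from baseline in the ALSFRS-R, ALSAQ-40, EQ-5D-5L, EQ-VAS, CBI and intracortical connectivity (SICI and ICF".
- **Timing (PROCEDURES).** T0 precedes allocation: "After the first evaluation (T0), the patients will be divided into two groups randomly". Follow-up is "at two weeks (T1), at two months (T2) and at six months (T3".
- **Clinical scores (STATISTICAL PLAN).** A repeated-measures ANCOVA includes "the baseline values of each score as covariate, to reduce possible effects of baseline impairment on clinical score changes over time".
- **TMS parameters (next paragraph of the same section).** "To assess the effect of tDCS treatment on TMS parameters we will use a two-way mixed ANOVA with TIME" at four levels (T0 to T3) and TREATMENT between subjects. No covariate is named, and no reason is given for the difference.
- **Post hoc tests.** "When a significant main effect was reached", Bonferroni-corrected tests compare the groups at each visit. The plan does not say whether they compare raw levels or changes.
- **Size and allocation.** "The proposed sample size of 30 patients should be adequate to achieve the main objective of the study"; real "or sham stimulation for 5 days/week for 2 weeks, in a 2:1 ratio respectively". That is 20 real and 10 sham.

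**The concern.** The plan accepts the case for baseline adjustment on the clinical scores and then leaves it out for the two neurophysiological endpoints. Having T0 as a level of TIME is not the same as adjusting for it, and each test in the ANOVA treats T0 differently:

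- The TIME x TREATMENT interaction compares changes from T0. This subtracts the whole T0 difference, when only the fraction rho of it is expected to persist.
- The post hoc visit comparisons, if made on raw levels, subtract none of it.
- The TREATMENT main effect averages in T0, where no treatment effect can exist.

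At stake are the width of the intervals for SICI and ICF, and whether their estimates can be trusted given the T0 imbalance actually seen. In a group of 10 against 20, that imbalance may not be small.

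**Working it through.** **Inputs from the documents.** 30 patients, 2:1 allocation (20 and 10), one visit before randomisation and three after. The documents give no SD, correlation, effect size or power for SICI or ICF, so there is no figure of the plan's to reproduce here. Its calculated total of 25 concerns the global MRC score.

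**Assumptions.** Equal SDs (results in SD units), compound symmetry with correlation rho = 0.3, 0.5 or 0.7, no dropout, an effect of 0.9 SD for the power figures, two-sided 0.05.

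**Step 1: likely size of the T0 imbalance.** SE = sqrt(1/20 + 1/10) = 0.387 SD. P(|Z| > 0.5/0.387) = 0.197. This step needs no assumption about rho.

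**Step 2: shift given a T0 imbalance D.** The expected follow-up difference, beyond any effect, is rho x D. A change contrast subtracts D, so it shifts by rho x D - D = -(1 - rho)D. A raw-level contrast shifts by rho x D, and a T0-adjusted contrast by 0. For D = 0.5 SD:

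| rho | change | raw level | T0-adjusted |
|---|---|---|---|
| 0.3 | -0.35 | +0.15 | 0 |
| 0.5 | -0.25 | +0.25 | 0 |
| 0.7 | -0.15 | +0.35 | 0 |

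**Step 3: single-visit variance.** The relative variances are 2(1 - rho) for change, 1 for raw level and 1 - rho^2 for adjusted. Estimating the slope multiplies the last by 27/26 on average at N = 30.

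- Adjusted/change = ((1 + rho)/2) x 27/26 = 0.675, 0.779, 0.883. It is 0.987 at rho 0.9 and reaches 1 at rho = 2 x 26/27 - 1 = 0.926.
- Adjusted/raw = (1 - rho^2) x 27/26 = 0.945, 0.779, 0.530. It reaches 1 at rho = sqrt(1/27) = 0.19.

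**Step 4: main effect.** An effect d constant over T1 to T3 enters as (0 + d + d + d)/4 = 0.75d.

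**Step 5: power.** Each row uses the same form of test on both sides, so only the covariate differs. Adjusted power is averaged over the random T0 imbalance.

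- (a) Noncentral t: variance 2(1 - rho), 28 df, against 1 - rho^2, 27 df.
- (b) Noncentral t: variance (4/3)(1 - rho), 28 df, against (1 + 2rho)/3 - rho^2, 27 df.
- (c) and (d) Noncentral F(3,26) on changes with covariance (1 - rho)(I + J), against F(3,25) with covariance (1 - rho)I + (rho - rho^2)J, where I is the 3 x 3 identity matrix and J the 3 x 3 matrix of ones.

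| Test | Change, % (rho 0.3/0.5/0.7) | T0-adjusted, % | Gain, points |
|---|---|---|---|
| (a) One visit, 1 df | 47.5/61.2/82.5 | 63.5/71.9/86.8 | 16/11/4 |
| (b) T1-T3 mean, constant effect | 64/78/94 | 91/93/98 | 27/14/3 |
| (c) Joint 3 df, constant effect | 44/59/83 | 76/79/90 | 32/20/8 |
| (d) Joint 3 df, effect fading 0.9/0.45/0 SD | 41/55/79 | 50/60/80 | 9/5/1 |

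At rho 0.8 the gain is 1 point in (a) and nil in (d).

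**Step 6: simulation.** With 20,000 trials per setting, these powers were reproduced within about 1 point, and every test rejected in 4.7% to 5.1% of trials under the null. The slopes of the estimate on the T0 imbalance were about -0.7/-0.5/-0.3 (change), 0 (adjusted) and 0.3/0.5/0.7 (raw).

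**The case against.** **The planned analysis is valid and matches the endpoint.** With T0 as a TIME level, the interaction tests differential change, which is what the endpoint definition asks for. It is unbiased over randomisation and keeps its type I error. This stands: the bias is conditional on the imbalance seen, and the matter is one of efficiency and of conditional bias on secondary endpoints.

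**Rows (c) and (d) are not the planned test.** The plan names Mauchly's test and Greenhouse-Geisser, so its interaction is the univariate F(3,84). Under the same assumptions that test has power 48/64/87% for the constant effect and 45/60/83% for the fading one, higher than the multivariate change test. Set against the multivariate adjusted figures, the gain drops to 28/15/4 and 5/0/-3 points. The figures are right, but the comparison mixes two forms of test. In simulation, an adjusted test that uses the same compound-symmetry structure reached about 80/83/92% and 55/66/85%. Like for like, the gain over the planned test is about 31/19/5 and 11/5/2 points (from unrounded values), close to rows (c) and (d).

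**The size rests on assumptions.** Rho, the effect and its shape are not in the documents, and the plan itself expects appreciable dropout. This stands as a limit on the size, not on the direction.

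**The 75% dilution is not caused by the missing covariate.** Correct: it comes from keeping T0 as an outcome level, as the clinical-score model also does. Taking only T1 to T3 as outcomes removes it.

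**SICI and ICF each have three interstimulus intervals, and the plan does not say how they are combined.** True, but this affects the planned ANOVA equally.

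**Conclusion.** The concern holds. SICI and ICF are defined as change from baseline but lack the covariate that the plan gives the clinical scores, and the plan gives no reason. The 20% chance of a T0 imbalance above 0.5 SD follows from the planned size and ratio alone. The rest depends on rho. For rho between about 0.19 and 0.93, adjustment is more precise at a single visit than both change scores and raw levels. Outside that range it costs about one degree of freedom against the better of the two. Against change scores the benefit is large at low rho and almost nil near 0.9. The effect size, compound symmetry and absence of dropout are also assumed. Nothing here touches the primary endpoint, the sample size or the type I error. The change should be made, but the trial's validity does not depend on it.

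**What to change.** In the STATISTICAL PLAN, replace the mixed ANOVA for SICI and ICF with a repeated-measures model that has T1, T2 and T3 as outcomes, the T0 value of the same parameter as covariate, and TREATMENT, TIME and TREATMENT x TIME as terms. Report the T0-adjusted group difference with its confidence interval at each visit, and keep the interaction so that a fading effect can be seen. State that the post hoc visit comparisons are these adjusted differences. Do not copy the clinical-score model as written, because it has T0 both as a TIME level and as a covariate.

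The cost is one or two sentences and about one residual degree of freedom, with no new data or visits. The plan already names mixed effects models for repeated measures for patients with missing values. The wording should be settled before anyone sees the T0 data by group.

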UO Neurologia 2 - AZIENDA SOCIO SANITARIA TERRITORIALE degli SPEDALI CIVILI DI BRESCIA

Direttore: [name]

1993). In this way, alterations of the intracortical inhibitory circuits have been identified in many neurological diseases, in particular in dystonia and in parkinsonism. The study of intracortical facilitation (ICF) is used to investigate the combined effect of secondary facilitation on inhibitory and excitatory mechanisms mediated by GABA_A and NMDA receptors respectively (Ziemann et al. 1998).

In particular, in patients suffering from ALS, a deficiency of SICI and ICF has been observed, due to an imbalance in the mechanisms of inhibition and cortical facilitation mediated by GABAergic and glutamatergic interneurons (Menon et al., 2015). Based on these premises, treatment with tDCS is proposed in patients with ALS.

TARGETS:

The aim of the study is to evaluate the long-term effects of tDCS on clinical, biological and neurophysiological parameters in patients with ALS.

In particular, the clinical and quality of life scales currently used in clinical trials on ALS will be used (ALSFRS-R, ALSAQ-40, CBI, EQ-5D-5L, muscle strength assessed with the MRC scale). Moreover, SICI and ICF protocols will be evaluated through TMS.

PROCEDURES:

Subjects enrolled at the Neurological Clinic will be enrolled with the diagnosis of probable ALS, laboratory-supported, or defined according to the current clinical criteria (World Federation of Neurology Revised El Escorial criteria - Brooks et al., 2000).

Subjects will sign an informed consent and will be subjected to a neurological clinical evaluation using the clinical and quality of life scales currently used in clinical trials on ALS (ALSFRS-R, ALSAQ-40, CBI, EQ-5D -5L, muscle strength evaluated with the MRC scale in different muscle groups).

Clinical assessment: Neuromuscular impairment will be quantified by the five-point MRC scale megascore (shoulder abductors, elbow flexors and extensors, wrist flexors, thumb opponent, hip flexors, knee flexors and extensors, and ankle dorsiflexors and extensors on both sides for a total of 100). Good reliability and reproducibility for manual muscle testing in patients with ALS have previously been shown.

Clinical status will be evaluated with the ALSFRS-R, quality of life with the amyotrophic lateral sclerosis assessment questionnaire-40-item scale (ALSAQ-40), EQ-5D-5L and EQ-VAS, while caregiver burden will be evaluated with the caregiver burden inventory (CBI).

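### Holm's step-down would keep the same family-wise error as the planned Bonferroni correction for the visit-by-visit arm comparisons and reject at least as much, a cheap gain of about 0 to 14 points of power at a single visit

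*Combined protocol and SAP*

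**What the plan says.** The STATISTICAL PLAN tests treatment over time with a two-way repeated-measures ANCOVA for the clinical scores and a two-way mixed ANOVA for the TMS measures. The visit comparisons come afterwards and are conditional, as the opening words "When a significant main effect was reached" show. For that case the plan states that "tests with Bonferroni correction for multiple comparisons will be conducted to analyze group-differences at respective time points". The plain reading is single-step Bonferroni. No step-down method is mentioned. The plan does not say whether the family is the three post-baseline visits (two weeks, two months, six months) or all four TIME levels including T0.

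The sample size rests on the ANCOVA and not on the visit tests: "considering alpha = 0.05 and the power (1- β) = 0.80", the requirement "is 25 total subjects using a repeated-measure ANCOVA study", with 30 planned. STUDY DESIGN allocates real to sham "in a 2:1 ratio respectively", so 20 and 10. TARGETS states the purpose: "The aim of the study is to evaluate the long-term effects of tDCS". END POINTS names change in global MRC score as primary but singles out no visit.

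**The concern.** Under single-step Bonferroni with three visits, each visit must reach 0.05/3 = 0.0167 however clear the other visits are. Holm relaxes the threshold for the remaining visits once one has been rejected, at no cost in family-wise error.

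The ANCOVA says whether the arms differ. The visit tests say when, so they bear on how long any difference lasts, which is what TARGETS asks about. With 20 against 10 patients, power at a single visit is limited. Some of it is given up to a correction for which a uniformly more powerful alternative exists. What is at stake is that a real difference at one visit may go undeclared although the trial has already rejected at another.

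**Working it through.** **1. The plan's own figure.** f = √(0.31/0.69) = 0.670. With a noncentral F, noncentrality N·f² and numerator df 2, power is 0.786 at N = 24 and 0.806 at N = 25. The stated 25 is reproduced. The plan does not state the df; 2 is the value that gives 25. No visit-specific effect and no Bonferroni step enters, so changing the visit-level correction cannot change this number.

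**2. Holm never rejects less.** Order the p-values p(1) ≤ p(2) ≤ p(3). Bonferroni compares each with 0.05/3. Holm compares them with 0.05/3 = 0.0167, 0.05/2 = 0.025 and 0.05, stopping at the first failure. If some p(j) ≤ 0.05/3, all smaller p-values are too, and each lies within its Holm threshold, so Holm reaches p(j) and rejects it. The first thresholds are equal, so both methods reject at least one visit in exactly the same trials.

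**3. Holm keeps the error rate.** With m true nulls among three, the smallest p-value among them has rank at most 3 − m + 1, so its threshold is at most 0.05/m. The chance of any false rejection is at most m × 0.05/m = 0.05, whatever the correlation between visits.

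**4. Size of the gain.** *From the documents:* 30 patients at 2:1, alpha 0.05, three post-baseline visits. *Assumed:* two-sided tests, visit effects in SD units, correlation between visits, and dropout. Two-sample t tests, 60,000 simulated trials per scenario, no gate. The table is for correlation 0.5. The last row assumes 20/18/16 against 10/9/8 patients at T1/T2/T3; the others have no dropout.

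| Effect at T1/T2/T3 (SD) | Bonferroni | Holm | Gain |
|---|---|---|---|
| Constant 1.34 | 0.812/0.814/0.810 | 0.882/0.883/0.882 | 0.070/0.069/0.072 |
| Moderate waning 1.34/1.0/0.67 | 0.814/0.525/0.226 | 0.833/0.601/0.347 | 0.019/0.076/0.121 |
| Steep waning 1.34/0.67/0.2 | 0.810/0.225/0.031 | 0.814/0.276/0.061 | 0.004/0.052/0.030 |
| Growing 0.67/1.0/1.34 | 0.227/0.522/0.814 | 0.348/0.599/0.833 | 0.121/0.077/0.019 |
| Peak at T2 0.67/1.34/1.0 | 0.226/0.809/0.523 | 0.347/0.828/0.598 | 0.121/0.019/0.075 |
| Constant 1.34, dropout | 0.810/0.754/0.692 | 0.869/0.834/0.797 | 0.059/0.080/0.105 |

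With correlation 0.8 included, the gain at a single visit ran from 0.000 (T1, steep waning) to 0.141 (T3, moderate waning). With no effect, family-wise error was the same for both methods: 0.046 at correlation 0.5 and 0.038 at 0.8 (no dropout). The chance of at least one rejection was identical in every scenario, for example 0.865 under moderate waning.

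**5. With the main-effect gate.** Setting: between-visit correlations 0.7/0.6/0.5, 27 df for a baseline covariate, effects 1.34/1.0/0.8 SD. T2 power was 0.52 with Bonferroni and 0.61 with Holm; T3 was 0.33 and 0.46. Requiring a treatment main effect at 0.05 first left these figures almost unchanged. Rejection at all three visits rose from about 0.25 to 0.42, and with a constant 1.34 SD from about 0.65 to 0.81. A rerun that fitted a simulated covariate gave powers 1 to 3 points lower and the same gains to within about a point.

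**6. If T0 is counted.** With four comparisons the first threshold is 0.05/4 = 0.0125. Holm's gain at T3 is then 6 points under moderate waning (0.191 to 0.255) and 1 point under growth (0.777 to 0.791).

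**The case against.** The strongest reply is that Bonferroni is valid, prespecified and has simple matching simultaneous intervals, and that these are gated follow-up tests. The question of treatment over time goes to the ANCOVA, on which the trial is powered. All of that stands, and it keeps the point small.

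Three stronger readings are tempting, and the documents do not support them.

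- *A reader might infer that the loss is greatest at six months.* That depends on the effect pattern. Holm's gain goes to the visits with larger p-values once another has been rejected. T3 gains most if the effect wanes moderately, or is constant with late dropout. If the effect grows, T3 gains about 2 points and T1 gains most; if it fades steeply, T3 gains about 3 points and T2 gains most. The background section speaks of an effect on disease progression, which could as well mean a widening difference.
- *A reader might take 1.34 SD, twice 0.67, as the plan's effect at a visit.* Doubling f holds for two equal groups in a one-df comparison. At 2:1 the conversion would be 0.67/√(2/3 × 1/3) = 0.67/0.471 = 1.42. In any case f(V) is a repeated-measures effect size and not a difference at one visit. The value is illustrative only.
- *A reader might infer that Bonferroni is what would hide a six-month effect.* In the gated waning example, T3 power under Holm is still 0.46, so the difference is missed in 54% of trials. The main limit is 20 against 10 patients.

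The interval objection also stands in part. Intervals kept at Bonferroni width may include zero at a visit that Holm declares significant.

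**Conclusion.** The point holds as a low-severity efficiency improvement. That Holm rejects at least as much at the same family-wise error is a mathematical fact and needs no assumption about this trial. The size of the benefit does need assumptions: about 0 to 14 points at a single visit, and about 16 to 17 points for rejection at all three visits in the two patterns examined (0.42 − 0.25 = 0.17; 0.81 − 0.65 = 0.16). These figures assume 20:10 patients, three comparisons, and illustrative effects, correlations and dropout, none of which the documents supply. Which visit benefits most cannot be known in advance. The ANCOVA, its sample size and the chance of at least one significant visit are untouched. Nothing in the plan is wrong on this point.

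**What to change.** In the post hoc sentence of the STATISTICAL PLAN, before unblinding, replace the Bonferroni correction with Holm's step-down over the three post-baseline visits. Compare the ordered p-values with 0.05/3, 0.05/2 and 0.05, and stop at the first failure. Keep the main-effect gate. For each clinical and TMS end point report Holm-adjusted p-values: 3·p(1), then the larger of that and 2·p(2), then the larger of that and p(3), each capped at 1. Naming T1, T2 and T3 as the family also settles the number of comparisons.

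The cost is one line of text, plus ordering three unadjusted p-values by hand. If simultaneous confidence intervals are shown, state that they are at Bonferroni width and may include zero at a visit that Holm declares significant. The change must be made before results are seen, because a correction chosen after seeing the p-values would not be credible.

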tDCS is a non-invasive, low cost and simple non-invasive brain stimulation method that is having an increasing diffusion and an increasingly numerous spectra of potential therapeutic applications such as, for example, post-stroke rehabilitation, depression and pain, which have already been established. Its effectiveness in modulating the excitability of the motor cortex in humans has been demonstrated (Nitsche et al., 2005). We therefore hypothesize that tDCS can have a positive effect on the clinical and quality of life scales, and restoration of neurophysiological parameters.

Literature data show that the application of the method according to the current safety guidelines (Iyer et al., 2005; Nitsche et al., 2003; Bikson et al., 2016) has little relevant side effects, among which mild tingling sensation during or after stimulation, moderate fatigue, mild itching sensation at the electrode sites, mild burning or pain, headache, nervousness, nausea, blistering at the electrode application points in rarer cases.

As for the TMS method, it is a non-invasive brain stimulation that allows the study of neurophysiological parameters that can provide information on the pathophysiological mechanisms involved in neurodegenerative diseases.

Literature data show that the application of the method according to the current safety guidelines has minor side effects: a certain number of subjects participating in TMS

CLINICA NEUROLOGICA - UNIVERSITA' DEGLI STUDI DI BRESCIA
UO Neurologia 2 - AZIENDA SOCIO SANITARIA TERRITORIALE degli SPEDALI CIVILI DI BRESCIA

Direttore: [name]

experiments (up to 20%) suffer from headaches or backaches, due to likely to an excessive muscle tension and a stiff position of the head and / or neck during TMS application. These effects are temporary and, in most cases, do not require any treatment.

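### The planned Spearman correlations between clinical improvement and neurophysiology say nothing about treatment arm; if arms are pooled, arm alone can produce a significant rho

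*Combined protocol and SAP*

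**What the plan says.** The whole specification is one sentence in STATISTICAL PLAN: "Spearman's rank-order correlations will be used to assess associations between the improvement in clinical scores and neurophysiological parameters". It does not give the analysis population, the visit, whether the neurophysiological parameter is a level or a change, or what is done about randomised arm.

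In the same section, TREATMENT is a between-subjects factor both in the repeated-measures ANCOVA for clinical scores and in the mixed ANOVA for TMS parameters. The correlation is the only planned analysis that brings the two outcome types together, and it is the one where arm is not mentioned.

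Two other places matter:

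- ETHICAL CONSIDERATIONS (RISK-BENEFIT) hypothesises that "tDCS can have a positive effect on the clinical and quality of life scales, and restoration of neurophysiological parameters", so an effect is expected on both variables being correlated.
- STUDY DESIGN allocates real and sham stimulation "in a 2:1 ratio respectively". With the planned 30 patients, that is 20 and 10.

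**The concern.** If treatment shifts both variables, the two arms form two displaced clouds of points. A correlation across all patients then picks up the line between the cloud centres. It does so even if, among patients given the same treatment, those whose SICI or ICF changed more did no better clinically. Such a rho restates the two arm differences that the ANCOVA and ANOVA already test.

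What is at stake is interpretation. This is the only planned analysis that could show whether neurophysiological change goes with clinical benefit in individual patients. The distortion grows with the treatment effects, so it would be largest in a successful trial, when readers would give the correlation most weight.

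**Working it through.** **1. The plan's own figure.** The documents give no number for the correlations. The nearest planning figure is the sample size for the global MRC score: "the sample size expected for two patient groups (real and sham) is 25 total subjects using a repeated-measure ANCOVA study", from partial eta squared 0.31, alpha 0.05, power 0.80 and one covariate.

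- f = sqrt(0.31 / 0.69) = 0.670, which agrees with the stated f(V) = 0.67.
- Noncentral F with lambda = f² × N, two groups, one covariate and 2 numerator df (three post-baseline visits) gives N = 25, power 0.80. The figure is reproduced.
- With 1 numerator df (a single between-arm contrast), the same formula gives N = 20, or 23 with lambda = f² × (N − 3). Neither is 25.

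So f(V) fits a multi-df repeated-measures effect better than a between-arm difference at one visit. If it is nevertheless read as a between-arm f at 2:1, then d = 0.67 / sqrt(2/3 × 1/3) = 0.67 / 0.4714 = 1.42. I use this only as an upper illustration.

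**2. Inputs for the check.**

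- From the documents: 30 patients at 2:1, hence 20 and 10; an effect expected on both kinds of measure.
- Assumed: normal outcomes with unit SD within arm; zero correlation within each arm; an arm shift of d on each measure; a two-sided test at 0.05. The 0.05 level is stated beside the baseline comparisons ("A p -value <0.05 will be considered significant"), and sidedness is not given.
- Assumed: every value of d. No effect size for SICI or ICF appears in the documents.

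**3. Expected pooled correlation.** With c = (20 × 10) / 30² = 0.222 and no within-arm link, the pooled product-moment correlation is

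r = c·d₁·d₂ / sqrt[(1 + c·d₁²)(1 + c·d₂²)].

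- d = 0.5 on both: 0.0556 / 1.0556 = 0.053
- d = 0.8 on both: 0.1422 / 1.1422 = 0.125
- d = 1.0 on both: 0.2222 / 1.2222 = 0.182
- d = 1.42 on both: 0.4481 / 1.4481 = 0.309
- either d equal to 0: r = 0

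The mean simulated Spearman rho matches closely: 0.05, 0.12, 0.18 and 0.31. Its sign depends on how the measures are scored.

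**4. How often the test is significant.** There were 20,000 simulated trials per scenario. The pooled Spearman was tested on N − 2 = 28 df. The adjusted version used ranks centred within arm and was tested on N − 3 = 27 df.

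| d clinical | d TMS | Pooled | Arm-adjusted |
|---|---|---|---|
| 0 | 0 | 5% | 5% |
| 1.42 | 0 | 5% | 5% |
| 0.5 | 0.5 | 6% | 5% |
| 0.8 | 0.5 | 7% | 5% |
| 0.8 | 0.8 | 10% | 5% |
| 1.0 | 1.0 | 16% | 5% |
| 1.42 | 0.8 | 18% | 5% |
| 1.42 | 1.42 | 40% | 5% |

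**5. Sensitivity to drop-out.** The plan gives no rate. With an assumed 20% loss (16 and 8 patients), d = 1.42 on both gives about 33% pooled against about 5% adjusted.

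**The case against.** **Pooling is not stated.** This stands. A reader might infer that the plan orders one correlation over all patients, but the sentence names no population. A correlation within the real-stimulation arm would also fit it, and would not carry this bias. What the documents support is that the plan is silent on arm and that its most natural execution is exposed.

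**The large percentages are not the planning scenario.** This stands too. A reader might infer that the trial is planned around a case where the pooled test is significant 40% of the time. The documents do not support that. The sample size concerns the MRC score only, no TMS effect is given, and d = 1.42 comes from a between-arm reading of f(V) that does not return 25 as a 1-df test. At moderate effects the excess is one or two percentage points, and with only one measure responding there is none.

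**These are not false positives in the strict sense.** Correct. If treatment moves both variables, they are associated across the trial population, and rejecting independence is right. The protocol writes of associations and claims no mechanism for this analysis. The error arises only when rho is taken to describe individual patients.

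**The stakes are low.** Also correct. No correlation appears under END POINTS, and both treatment models contain TREATMENT.

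What survives is narrower. The protocol hypothesises effects on both measures, its one analysis joining them does not address arm, and the standard adjustment removes the problem almost without cost.

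**Conclusion.** The point holds as a minor improvement to a supportive analysis. The plan does not say how arm enters the Spearman correlations. If they are run across both arms and tDCS affects both measures, a significant rho can arise with no patient-level link in either arm.

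The size depends on effects that the documents do not supply. It is negligible at d = 0.5 on both measures (6% against a nominal 5%), appreciable at 0.8 to 1.0 (10% to 16%), and about eightfold (40 / 5) in the upper illustration. These figures rest on 20 and 10 patients, normal outcomes, zero within-arm correlation and a two-sided 0.05 test.

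Nothing here touches the primary end point, the sample size or the tests of treatment effect.

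**What to change.** Replace the sentence in STATISTICAL PLAN with:

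> Associations between change from baseline in clinical scores and change from baseline in SICI and ICF at the same visit will be assessed with Spearman correlations partialled on TREATMENT, and also shown within the real-stimulation arm; they are exploratory, and unadjusted pooled correlations will not be interpreted as a patient-level link.

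This settles the role of arm, the definition of change, the pairing of visits and the status of the analysis. The exploratory label matters because six clinical scores (MRC, ALSFRS-R, ALSAQ-40, EQ-5D-5L, EQ-VAS, CBI) by two TMS measures give 6 × 2 = 12 correlations per visit, and the Bonferroni step covers only the post hoc group comparisons.

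The cost is one degree of freedom (27 instead of 28 with 30 patients) and no new data. The downside is low precision within the real-stimulation arm. By Fisher's z, at 80% power and two-sided 0.05, 20 patients can detect a correlation of about tanh(2.80 / sqrt(17)) = 0.59, against tanh(2.80 / sqrt(27)) = 0.49 for 30. The within-arm results should therefore be shown as estimates with intervals and not judged by significance.
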